In subjects receiving an intrathecal opioid in combination with another drug(s) prior to the enrollment of the study, the intrathecal opioid will be converted directly to the study medication (see the conversion scheme above) while the dose of the other drug(s) used in the combination should be kept the same.

The conversion will take place by removing the current intrathecal opioid therapy in the pump and then replacing the contents with study hydromorphone hydrochloride for intrathecal injection. At the discretion of the investigator the pump reservoir may be rinsed with preservative free sterile saline or study medication (hydromorphone hydrochloride for intrathecal injection).

01 August 2016 27 CONFIDENTIAL

² Conversion is based on mg-morphine equivalence such that for each 12 mg morphine sulfate the dose is converted to 1 mg hydromorphone hydrochloride.

³ Convert the opioid to mg-morphine equivalence dose first. Then convert to hydromorphone hydrochloride based on mg-morphine equivalent dose using the conversion scheme.

Dose adjustments may occur for any subject during the study, either on scheduled visits or unscheduled visits after study Day 1, as needed based on the following scheme:

Dose of	Maximum
Hydromorphone	Dose
Hydrochloride IT	Adjustment
0.1 to 0.5 mg/day	50 %
> 0.5 mg/day	25 %

As needed, additional intrathecal concomitant medications may be added to the therapy to optimize pain control (see Section 3.6.2).

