not exceeded. All medications administered must be recorded. At no time may a contraindicated treatment (see Section 3.6.3) be administered in combination with hydromorphone hydrochloride. Subjects will be assessed for pain intensity using a VASPI instrument at each study visit.

Subjects will be evaluated for side effects and clinical complications associated with the use of intrathecal hydromorphone hydrochloride. Signs and symptoms of a suspected granuloma will be monitored; examples of these include but are not limited to radicular pain and loss of drug efficacy.

If there are signs or symptoms identified which may indicate an inflammatory mass formation, an MRI (with and without contrast) or CT myelogram will be performed (with consent of the subject) to evaluate the potential presence of a granuloma as opposed to other catheter related problems that may result in reduced delivery or clinical symptoms. Events will be classified by duration, and concentration of intrathecal hydromorphone hydrochloride. Events that may be related to a granuloma will be classified as confirmed granuloma or suspected granuloma.

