5.0 SAFETY ASSESSMENTS

5.1 Collection of Adverse Events Data

Data regarding treatment-emergent AEs will be collected in this study. Treatment-emergent AEs are events that are not present at baseline, or if present at baseline, have worsened in severity. AEs will be assessed at each study visit from the time of study drug administration, during optional titration days, and for the long-term safety period starting on Study Day 1 through the final visit. AEs assessed by the Investigator as related to study drug and "ongoing" at the final scheduled study visit will be monitored by the Investigator until resolved or stabilized.

Protocol CNS-HYD202US

Version: 7.0

Each subject will be observed and queried by the Investigator or his/her designee at each study visit for any continuing AEs or new AEs since the previous visit. If an AE occurs between study visits, regardless of causal relationship to study drug and in the opinion of the Investigator, requires a study visit for full evaluation, the subject will be asked to return to the site for an unscheduled visit.

Any AE reported by the subject or noted by the Investigator or his/her designee will be recorded. The following information will be recorded for each AE: description of the event, date and time of onset, date and time of resolution, severity, causal relationship to study drug, outcome, action taken with the study drug and any treatment given.

All abnormal changes from baseline in physical examination findings including vital signs will be collected, graded with regards to severity or clinical significance, assessed for causal relationship, and will be recorded.

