5.3 Vital Signs and ECG

Systolic and diastolic blood pressure, radial pulse, breathing rate and temperature will be obtained at baseline and each study visit and recorded. All vital signs will be obtained in a semi-recumbent position.

An ECG will also be obtained at screening to assess any cardiovascular abnormalities for the purposes of determining eligibility for this trial.

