8.0 EFFICACY

There is no efficacy endpoint in this trial given the open-label nature of the study. Subjects will be given a VASPI at scheduled time periods and generally during visits to the clinical site.

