Appendix A: Schedule of Study Procedures									

Table A-1: Schedule of Study Procedures

Study Procedure					Visit Schedule								
Study Day ^a	Screening Days -14 to 1 ^b	Baseline Days -3 to 1 ^b	Baseline for HYD201US Subjects ^b	Optional Titration Days ^{b,c}	Day 1 ^{b,d}	Day 28	Day 56	Day 80	Day 104	Day 160	Day 216	Day 286	Final Study Visit Day 365
Signed Informed Consent	X ^e		X										
Medical History ^f	X		*										
Complete physical exam ^g	X		*										X
Vital signs and Weight ^g	X	X	*	X	X	X	X	X	X	X	X	X	X
Urine pregnancy test ^g	X	X	X										X
ECG ^g	X		X										
CBC, CMP, Urinalysis ^g	X		X										
Concomitant medication assessment	X	X	*	X	X	X	X	X	X	X	X	X	X
Adverse event assessment	X	X	*	X	X	X	X	X	X	X	X	X	X
Hydromorphone Hydrochloride Pump Dose Adjustment and Refills h,I,l			X	X	X	X	X	X	X	X	X	X	X^{l}
Oral Opioid			X										·
Clinical evaluation for Granulomas ^j	X		*		X	X	X	X	X	X	X	X	X
VASPI Assessment ^k	X	X	*	X	X	X	X	X	X	X	X	X	X
COWS Assessment ^k		X	*	X									X
BPI^k		X	*			X		X		X		X	X
PGIC ^k		X	*			X		X		X		X	X

- a. Study Day is based on Day 1 defined as the first day a subject achieves a therapeutic dose of hydromorphone therapy. There is no Day 0 in this trial. Optional titration days for subjects below therapeutic levels will not be counted towards the 365 day study period. All visit days are +/- 7 days during the long-term extension phase of the study. Additional unscheduled visits may be scheduled to make dose adjustments or prescribe oral medication to manage pain and withdrawal symptoms as deemed appropriate by the investigator.
- b. Screening period is 14 days. Screening, Baseline and/or Initiation of Dosing (ie, Optional Titration Day or Day 1) visits may be combined. For subjects entering the CNS-HYD202US clinical trial that are transitioning from the CNS-HYD201US efficacy trial, these subjects will not be required to repeat Screening. For these subjects the last day of the CNS-HYD201US trial will be considered the first day (either optional titration day or Day 1) of the CNS-HYD202US trial. Baseline assessments will be completed as part of the final day (Day 119 or Treatment Failure day) and only additional activities or tests shown on the Schedule of Events (shown in table of events as "X") for these subjects are required to enter the CNS-HYD202US trial. Tests that are done as part of the final visit of the CNS-HYD201US trial and will not be repeated in this study are shown in the table with a "*".

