9.5.3 Vital Signs and Weight

Systolic and diastolic blood pressure (mmHg), radial pulse (beats/minute), respiratory rate (breaths/minute), weight (kg), and temperature (°C) will be obtained at baseline and each study visit and recorded on the eCRF.

All vital signs and weight measurements as well as change from Baseline for these measurements will be summarized at each visit. A listing of weight and vital signs will also be provided.

The number and percentage of subjects with potentially clinically significant vital signs will be summarized at each visit. A listing of subjects with potentially clinically significant vital signs will also be presented. Table contains the criteria for identifying potentially clinically significant vital sign vital sign values.

Vital Sign Parameter	Criteria
Systolic Blood Pressure (mmHg)	>160 mmHg or increase of ≥20 mmHg from baseline
Systolic Blood Pressure (mmHg)	<95 mmHg or decrease of ≥20 mmHg from baseline
Diastolic Blood Pressure (mmHg)	>110 mmHg or increase of ≥15 mmHg from baseline
Diastolic Blood Pressure (mmHg)	<50 mmHg or decrease of ≥15 mmHg from baseline
Heart Rate (bpm*)	>100 bpm or increase of \geq 15 bpm from baseline
Heart Rate (bpm*)	<50 bpm or decrease of ≥15 bpm from baseline
Weight (kg) Gain	>10% weight increase
Weight (kg) Loss	>10% weight decrease

 Table 2:
 Criteria for Identifying Potentially Clinically Significant Vital Sign Values

*bpm = Beats per minute

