9.6 Secondary Endpoints

9.6.1 Visual Analogue Scale of Pain Intensity (VASPI)

The VASPI will be a single question assessing how severe a subject's pain is 'right now'.

Scoring is based on the continuous visual analog scale (measured in mm) ranging from no pain at the start of the scale to unbearable pain at the end of the scale. VASPI will be assessed at Baseline and each study visit, including the final visit. The VASPI scores, as well as change from baseline, will be summarized at each visit. All assessments will be listed.

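### SAP 9.5.3 counts potentially clinically significant vital signs visit by visit only, so Table 14.3.5.2 cannot show how many subjects were ever flagged and gives unscheduled readings no stated place

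*Protocol*

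**What the plan says.** **Collection.** Protocol 5.3: "Systolic and diastolic blood pressure, radial pulse, breathing rate and temperature will be obtained at baseline and each study visit and recorded". Protocol 3.1 uses the same phrase for pain: "Subjects will be assessed for pain intensity using a VASPI instrument at each study visit".

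**Unscheduled visits.** These are prompted by events. Protocol 3.1: "Dose adjustments may occur for any subject during the study, either on scheduled visits or unscheduled visits after study Day 1". Protocol Appendix A, footnote a: "Additional unscheduled visits may be scheduled to make dose adjustments or prescribe oral medication to manage pain and withdrawal symptoms". Protocol 9.4 adds the assessment of possible complications. Under Protocol 5.1, if an adverse event between visits "requires a study visit for full evaluation, the subject will be asked to return to the site for an unscheduled visit". The schedule (Protocol Table A-1, SAP Table 1) has no column for unscheduled visits.

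**Analysis.** SAP 9.5.3: "The number and percentage of subjects with potentially clinically significant vital signs will be summarized at each visit". The criteria are in SAP Table 2 and the output is Table 14.3.5.2 in SAP Appendix A. A listing of flagged subjects is also planned. SAP 9.6.1 treats pain the same way: "The VASPI scores, as well as change from baseline, will be summarized at each visit". The SAP has no visit windows, no rule for assigning an unscheduled reading to a visit, and no any-time or worst-value row.

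**The concern.** The objective is 12-month safety. For vital signs, the natural subject-level question is how many subjects met a criterion at least once on treatment. A table of separate visit percentages does not answer it, because a low figure at every visit fits both a small group flagged repeatedly and a much larger group flagged once each.

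A second gap adds to this. Unscheduled visits happen because something needs attention, so their readings are not a random sample of a subject's year. The SAP does not say where they go. A programmer must either leave them out of the by-visit table or invent a rule.

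**Working it through.** The plan states no figure on this point, so there is nothing to reproduce. The visit days come from the documents. Every flag rate below is an assumption.

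**1. Scheduled visits after Day 1.** Days 28, 56, 80, 104, 160, 216, 286 and 365 make 8 visits. The gaps from Day 1 are 27, 28, 24, 24, 56, 56, 70 and 79 days. With the ±7-day window at both ends, the longest gap can reach 79 + 14 = 93 days. An unscheduled reading may be the only one in such an interval.

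**2. What the by-visit table leaves open.** Let p be the share flagged at each of 8 visits, with every subject attending all of them.

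- Same subjects each time: any-time share = p.
- Visits independent: any-time share = 1 − (1 − p)^8.
- No subject flagged twice: any-time share = 8p.

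With p = 3% assumed:

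- same subjects: 3%
- independent: 1 − 0.97^8 = 21.6%
- no repeats: 8 × 3% = 24%

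All three produce the same by-visit table. This gap exists even if there are no unscheduled readings.

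**3. Adding unscheduled readings.** Suppose each subject has u unscheduled visits, each flagged with probability q, independently of the rest. Then the any-time share = 1 − (1 − p)^8 × (1 − q)^u. For u = 0.5 this is a rough average.

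| p per scheduled visit | Scheduled only | u = 0.5, q = 10% | u = 1, q = 20% | u = 2, q = 30% |
|---|---|---|---|---|
| 5% | 33.7% | 37.1% | 46.9% | 67.5% |
| 20% | 83.2% | 84.1% | 86.6% | 91.8% |

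The addition runs from about 1 percentage point to about 34. The documents give neither the frequency of unscheduled visits nor the flag rates, so they do not fix the size.

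**4. Other routes into the tables.** The statistical methodology in the protocol synopsis has clinically meaningful vital-sign abnormalities analysed as adverse events. SAP 9.5.1 defines treatment-emergent events by onset or worsening after first treatment and counts them per subject, not per visit. What can be missed is therefore a value that meets a Table 2 criterion but is not reported as an adverse event.

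**The case against.** The strongest reply is that little is lost. The primary endpoint is adverse events and serious adverse events, which are captured whatever the visit type. Clinically meaningful abnormalities join those tables, and Protocol 5.1 has abnormal changes in vital signs graded and assessed for causality. SAP 8.7 lists all eCRF data, and SAP 9.5.3 lists flagged subjects. Readings at early discontinuation belong to the final visit (Protocol 9.5). No formal testing is planned. All of this stands and keeps the point modest. It does not supply the any-time count, and a listing is not a summary.

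Two stronger readings are tempting.

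- *Unscheduled readings stay out of every table.* A reader might infer this from the by-visit wording and the missing column. The SAP does not exclude them; it is silent. Collection at unscheduled visits is itself a fair reading of Protocol 5.1 and 5.3, not an explicit instruction.
- *By-visit VASPI means make pain control look better than it was.* The documents do not support this. Protocol 8.0 says "Subjects will be given a VASPI at scheduled time periods and generally during visits to the clinical site", but footnote k to Appendix A ties the instrument to specified visits. Nor does omitting flare-driven readings by itself bias a scheduled mean, because scheduled visits that fall independently of flares sample them in proportion to time. With an assumed 0.5 to 2 seven-day flares a year of 20 to 30 mm, the time-averaged effect is 0.5 × 7/365 × 20 = 0.19 mm to 2 × 7/365 × 30 = 1.15 mm, and the scheduled mean carries it. Peak pain between visits is a different question from the stated endpoint of change over time.

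**Conclusion.** The point holds for the PCS vital-sign table. As written, Table 14.3.5.2 cannot show the share of subjects who ever met a criterion, and the SAP does not say how unscheduled vital signs are handled. At an assumed 3% per visit over 8 fully attended visits, the any-time share is 3% with complete overlap and about 22% under independence, before unscheduled readings. What those readings add cannot be computed from the documents.

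The consequence is limited to values that meet Table 2 criteria without being reported as adverse events. The documents do not support a general conclusion that safety is made to look better, nor one that the VASPI means are biased.

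**What to change.** In SAP 9.5.3 and Table 14.3.5.2, add for each criterion a row 'any post-baseline visit, including unscheduled', counting each subject once per criterion. Show the number of readings per subject beside it. State which readings count as post-baseline, including those on optional titration days. Keep the by-visit rows on scheduled visits, and say so.

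The database was locked on 07 February 2018 (SAP 8.4), so label the row as added after lock. SAP Appendix A allows additions to the table list.

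The cost is a few sentences and some programming on data already listed; no new collection is needed. The downside is that the any-time figure looks less favourable and rises with the number of visits, which is why the reading count belongs beside it.

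Worst post-baseline VASPI is at most an optional exploratory summary. It is sensitive to measurement noise and visit count, and SAP 8.4 says the VASPI data were not cleaned or queried after 11 September 2017. A count of unscheduled visits made for pain is not proposed, since nothing in the documents shows that the eCRF records the reason for such a visit.

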3.2 Study Endpoints

3.2.1 Primary Endpoint

Safety of intrathecal hydromorphone hydrochloride as assessed through collection of AEs and SAEs during the conduct of the trial. Particular attention will be paid to:

- The rate of confirmed granulomas verified by MRI (with and without contrast), CT myelogram or by surgery.
- The rate of suspected granulomas that cannot be verified by MRI (with and without contrast), CT Myelogram or surgery.

3.2.2 Secondary Endpoints

The following secondary endpoints will be assessed. Each of these endpoints will be evaluated at each study visit.

- Change in Visual Analog Scale Pain Intensity (VASPI) over time.
- Change in the Brief Pain Inventory (BPI) (1, 2) over time.
- Change in the Patient Global Impression of Change (PGIC) (3) over time.

3.3 Diagnosis of an Inflammatory Granuloma

The use of intrathecal morphine has been associated in rare cases with a granuloma at the catheter tip that can result in serious neurological impairment, including paralysis. These events have been reported infrequently with hydromorphone hydrochloride and are more commonly associated with use of combinations of compounded drugs or high concentration formulations.

01 August 2016 29 CONFIDENTIAL

Nevertheless, the potential for a granuloma or mass will be assessed at each visit to the investigator.

Clinical signs and symptoms that may indicate a granuloma include:

- A sudden decrease in therapeutic response requiring increased daily doses that is not attributed to other assignable causes (eg, mechanical failures, catheter movement or catheter blockages).
- Change in the character, quality, or intensity of the subjects pain (ie, is less well managed).
- o Unexplained pain at the dermatomal level of the catheter tip.
- Unexplained neurological deficit or dysfunction that could be caused by mass effect at the spinal level of the catheter tip.

If in the opinion of the investigator there is a reasonable probability that the subject may be experiencing a granuloma, an MRI (with and without contrast) or CT myelogram will be requested. All MRIs (with and without contrast) and CT myelograms will be assessed by a single central independent radiologist who will be blinded to the subject's history. The criteria used by the primary investigator to detect a potential granuloma will be recorded.

For the purpose of this study to establish that there is a definite granuloma, an MRI (with and without contrast) or CT myelogram must demonstrate an intradural extra-medullary mass near the catheter tip and be confirmed by an independent blinded radiologist. If only clinical signs are detected, but the granuloma or mass cannot be verified by MRI (with and without contrast) or CT myelogram, and no other cause can be determined, the event will be classified as a suspected granuloma.

3.3.1 Treatment of an Inflammatory Granuloma

If a granuloma is detected early in its clinical course, depending upon an individual subject's clinical condition, intra-spinal therapy may be continued after one of the following interventions:

- o Withdraw the catheter to a level below the granuloma.
- Remove the involved catheter and replace it with a new catheter positioned below the granuloma.
- Lower the IT dose or replace with saline until the inflammatory mass resolves.
- Disconnect the involved catheter from the connector (two-piece catheter), or transect the involved catheter above the level of the lumbodorsal fascia (one-piece catheter) leaving the intra-spinal catheter segment undisturbed. Ligate the exposed end of involved catheter to prevent CSF loss. Implant a new catheter with its tip below the granuloma, and connect the new catheter to the proximal (pump) catheter segment.

Prompt open surgical removal of the granuloma or decompression of the spinal cord should

01 August 2016 30 CONFIDENTIAL

only be considered in subjects who have a significant or progressive neurological deficit.

3.4 Measures to Minimize Bias

3.4.1 Blinding

This is an open-label, single-arm safety trial. As such there is no blinding.

3.4.2 Randomization/Assignment to Study Drug

Each subject entered into the trial will be assigned a subject number consisting of a two-digit site number and three-digit sequential subject number (SS-XXX). This number will be used for the entire duration of the trial. There is no randomization in this trial.

3.5 Study Drugs

3.5.1 Rationale for Doses and Dosing Regimen

3.5.1.1 Titration to a Therapeutic Dose of Hydromorphone Hydrochloride

For subjects entering the trial already on a therapeutic dose of another intrathecal hydromorphone hydrochloride, the hydromorphone hydrochloride will be replaced by the study drug (hydromorphone hydrochloride for intrathecal injection) on a 1:1 basis without dose adjustment or optional titration days. The subject is considered at a therapeutic dose and will start the study on Day 1.

Subjects who are converted directly to the study drug based on the 1:6 morphine-equivalence ratio are, by definition, at a therapeutic dose and must start the study on Day 1 without titration Dose adjustments may be performed at subsequent visits, based on the investigator discretion (see Section 3.1).

For subjects converted using the 1:12 ratio, due to safety considerations, the conversion will be followed by up to five (5) optional titration days (Titration Days A, B, C, D and E) to achieve a therapeutic dose before starting Day 1. These optional titration days may be three (3) to fourteen (14) days apart.

The conversion will take place by removing the current intrathecal opioid therapy in the pump and then replacing the contents with study hydromorphone hydrochloride for intrathecal injection. At the discretion of the investigator the pump reservoir may be rinsed with preservative free sterile saline or study medication (hydromorphone hydrochloride for intrathecal injection).

Subjects who are naïve to intrathecal analgesics will have the pumps filled initially with a 2 mg/mL hydromorphone hydrochloride for intrathecal injection. Naïve subjects will be initiated on a dose between 0.1 mg/day and 0.5 mg/day, based on their current opioid dose and the

discretion of the investigator. These subjects will be allowed up to five (5) optional titration days to achieve a therapeutic dose of hydromorphone prior to starting the long term safety period on Day 1 of this study. These optional titration days may be three (3) to fourteen (14) days apart. Prior to a dose adjustment above 1 mg/day, the pump should be drained and refilled with 10 mg/mL hydromorphone hydrochloride undiluted and pump speed adjusted to achieve the target dose. Dose adjustments may continue as needed to optimize the therapy. After achieving a therapeutic dose of hydromorphone hydrochloride, other permitted drug products (see Section 3.6.2) may be added to the pump to optimize analgesia for these subjects if needed.

Subjects continuing on therapy from the CNS-HYD201US trial may remain at their current dose of hydromorphone hydrochloride or may have a dose adjustment if clinically indicated, beginning at Day 1 of this study. Subjects who were titrated off of hydromorphone hydrochloride as part of the CNS-HYD201US control arm will be titrated back to a therapeutic dose using one or more optional titration days prior to Day 1 of this study.

A maximum dose 10 mg/day intrathecal hydromorphone hydrochloride is permitted at any time during this study. For subjects on PTM dosing regimens, the maximum daily dose will include the combined continuous dose and the allowed maximum PTM dose. All subjects should be contacted by telephone 24 hours after initiating study medication of hydromorphone hydrochloride.

3.5.1.2 12-Month Course of Treatment

After the initial titration period, if needed, subjects will start on Day 1 of this trial and remain on therapy for an additional 365 days of hydromorphone hydrochloride treatment. After the initial titration and during the 365 day continuous dosing period run in period, dose adjustments are permitted either upward or down as deemed necessary by the investigator, provided that the maximum dose of 10 mg/day is not exceeded. During this long term evaluation period subjects will visit the clinic as outlined in the Schedule of Events (Appendix A) for evaluations, but may come back sooner if necessary to adjust the daily dose or for any safety related reason.

As needed, additional concomitant medications and intrathecal therapies may be added to the therapy to optimize pain control of the compound and dose (see Section 3.1).

